7.3.4. Completion and transmission of ADR report to GSK Vaccines

Once the physician is aware of an adverse drug reaction that the subject experienced, he/she should report to GSK.

The physician (or his/her designee) should record as all detailed information obtained about the adverse drug reaction as possible in the section for ADR Report Form completely and send to GSK. If the physician does not have all information about the adverse drug reaction, he/she does not wait for additional information before completing the form and notifies to GSK. When obtaining additional information, the report form should be updated.

The physician sends ADR Report Form to the Contact for Reporting SAEs, ADRs and Pregnancies that collects an adverse drug reaction by fax or e-mail.

7.3.5. Completion and transmission of pregnancy reports to GSK Vaccines

Once the physician becomes aware that a subject is pregnant, the physician (or designee) must complete a Pregnancy Report Form and fax or e-mail it to the Contact for Reporting SAEs, ADRs and Pregnancies (refer to the Sponsor Information Sheet) within 2 weeks, if possible.

The Pregnancy Report Form will always be completed as thoroughly as possible with all available details and then dated and signed by the physician (or designee), if possible. Even if the physician does not have all information regarding the pregnancy, the form should still be completed and forwarded to GSK within 2 weeks, if possible. Once additional relevant information is received, the form will be updated and forwarded to GSK within 2 weeks, if possible.

In absence/dysfunction of facsimile equipment, the Contact for Reporting SAEs, ADRs and Pregnancies should be notified by telephone within 2 weeks, if possible. As soon as the facsimile equipment is working again, the physician (or designee) must fax the Pregnancy Report Form to the Contact for Reporting SAEs, ADRs and Pregnancies (refer to the Sponsor Information Sheet) within 2 weeks, if possible.

7.3.6. Regulatory reporting requirements for serious adverse events

The physician will promptly report all SAEs to GSK in accordance with the procedures detailed in Section 0. GSK Vaccines has a legal responsibility to promptly notify, as appropriate, both the local regulatory authority and other regulatory agencies about the

safety of a product surveillance. Prompt notification of SAEs by the physician to the Contact for Reporting SAEs, ADRs and Pregnancies is essential so that legal obligations and ethical responsibilities towards the safety of other subjects are met.

7.4. Follow-up of adverse events, serious adverse events, and pregnancies

7.4.1. Follow-up of adverse events and serious adverse events

After the initial AE/SAE report, the physician is required to proactively follow each subject and provide further information to GSK Vaccines on the subject's condition.

All SAEs documented at a previous visit/contact and designated as not recovered/not resolved or recovering/resolving will be reviewed at subsequent visits/contacts until the end of the drug use investigation.

All AEs documented at a previous visit/contact and designated as not recovered/not resolved or recovering/resolving will be reviewed at subsequent visits/contacts until 21 days after vaccination.

Physicians will follow-up subjects:

- With SAEs or subjects withdrawn from the study as a result of an AE, until the event has resolved, subsided, stabilised, disappeared, or until the event is otherwise explained, or the subject is lost to follow-up.
- Or in the case of other non-serious AEs, until or they are lost to follow-up.

Clinically significant laboratory abnormalities will be followed-up until they have returned to normal or a satisfactory explanation has been provided. Additional information (including but not limited to laboratory results) relative to the subsequent course of such abnormalities noted for any subject must be made available to the study monitor.

GSK Vaccines may request that the physician perform or arrange for the conduct of additional clinical examinations/tests and/or evaluations to elucidate as fully as possible the nature and/or causality of the AE or SAE. The physician is obliged to assist. If a subject dies during participation in the drug use investigation or during a recognised follow-up period, GSK Vaccines will be provided with a copy of any available post-mortem findings, including histopathology.

7.4.2. Follow-up of pregnancies

Pregnant subjects will be followed to determine the outcome of the pregnancy, if possible. At the end of the pregnancy, whether full-term or premature, information on the status of the mother and child will be forwarded to GSK, if possible. Generally, the follow-up period does not need to be longer than 6 to 8 weeks after the EDD, if possible.

7.5. Treatment of adverse events

Treatment of any AE is at the sole discretion of the physician and according to current good medical practice. Any medication administered for the treatment of an AE should be recorded in the subject's CRF.

8. EFFICACY ASSESSMENT

Efficacy of a vaccine is assessed by the reduction in the occurrence of the disease targeted by the vaccine in people immunized with the vaccine comparing to those not vaccinated. A drug use investigation will be implemented within the routine clinical setting to collect unspecified safety and efficacy data of the drug through the study period. It will be difficult for the physicians to request the subject after vaccination to revisit for assessment and/or laboratory testing not deemed necessary in normal clinical practice due to the physical, logistic, and economic burden to the subject. Therefore, the efficacy assessment of *Fluarix Tetra* would likely be omitted in this drug use investigation.

9. SUBJECT COMPLETION AND WITHDRAWAL

9.1. Subject completion

A subject who is available for the concluding follow-up contact 21 days after receiving *Fluarix Tetra* is considered to have completed the drug use investigation.

9.2. Subject withdrawal

Subjects who are withdrawn because of SAEs/AEs must be clearly distinguished from subjects who are withdrawn for other reasons. Physicians will follow subjects who are withdrawn as result of a SAE/AE until resolution of the event (see Section 7.3).

Withdrawals will not be replaced.

From an analysis perspective, a 'withdrawal' from the drug use investigation refers to any subject who was not available for the concluding contact foreseen in the protocol.

All data collected until the date of withdrawal/last contact of the subject will be used for the analysis.

A subject is considered a 'withdrawal' from the drug use investigation when no study procedure has occurred, no follow-up has been performed and no further information has been collected for this subject from the date of withdrawal/last contact.

Physicians will make an attempt to contact those subjects who do not return for scheduled visits or follow-up.

Information relative to the withdrawal will be documented in the CRF. The physician will document whether the decision to withdraw a subject from the study was made by the

subject/subject's parent(s)/LAR(s) or by the physician, as well as which of the following possible reasons was responsible for withdrawal:

- SAE
- Non-SAE
- Protocol violation (specify)
- Consent withdrawal, not due to an AE
- Moved from the study area
- Lost to follow-up
- Death
- Other (specify)

10. DATA EVALUATION: CRITERIA FOR EVALUATION OF OBJECTIVES

10.1. Endpoints

- Occurrence of expected and unexpected AEs during the 21 days (Day 0 to Day 20) follow-up period after vaccination.
- Occurrence of SAEs starting from the date of vaccination in the drug use investigation up to 21 days (Day 0 to Day 20) after vaccination of the subject in the drug use investigation.

10.2. Sample size consideration

According to MFDS requirement, at least 600 evaluable subjects should be recruited for each drug use investigation. Therefore, max 1440 subjects (720 vaccinees \geq 3 years old and above and 720 vaccinees between 6-35 months old) will be enrolled through the drug use investigation period. We assume that 20% of enrolled participants might drop out (depending on the status of actual enrolment), then the plan can be adjusted accordingly.

Table 4 presents the exact two-sided 95% CI for a sample size of 600 subjects for each group²⁾.

Table 4 Exact two-sided 95% CI for the percentage of subjects reporting at least one symptom with a sample size of 600 subjects

Observed rate expressed as a percentage (number of subjects reporting at least one symptom *)	Exact two-sided 95% CI for this observed rate for a sample size of 600 subjects	
	Lower limit (LL)	Upper limit (UL)
1%	0.4	2.2
2%	1.0	3.5
3%	1.8	4.7
4%	2.6	5.9
5%	3.4	7.1

Observed rate expressed as a percentage (number of subjects reporting at least one symptom *)	Exact two-sided 95% CI for this observed rate for a sample size of 600 subjects	
	Lower limit (LL)	Upper limit (UL)
10%	7.7	12.7
15%	12.2	18.1
20%	16.9	23.4

* The symptom could be any one of expected AE, unexpected AE, or SAE.

10.3. Drug use investigation cohort to be evaluated

10.3.1. Total vaccinated cohort

The total vaccinated cohort will include all subjects who receive *Fluarix Tetra* and participated in the drug use investigation:

- When subjects are vaccinated out of label and physicians already gathered the information, this information will be added in the PMS report separately.

10.3.2. Total Safety cohort

The total Safety cohort will include all subjects who receive *Fluarix Tetra*, participated in the drug use investigation and provide post vaccination safety data.

10.4. Conduct of analyses

Any deviation(s) or change(s) from the original statistical plan outlined in this protocol will be described and justified in the final report.

10.4.1. Sequence of analyses

Analysis will be performed bi-annually for the first two years and annually for the remaining follow-up years for each study group (3 years old and above, and 6-35 months old children). (based on pre defined cut-off date for enrolment). A comprehensive analysis, pooling all years will be performed at the end of the drug use investigation. The analysis, including individual data listings, will be based on the cohort for vaccinated subjects for whom the drug use investigation conclusion page has been received at GSK before the pre-defined cut-off date. All periodic and final statistical analysis reports will be sent to the GSK VCSP and to MFDS.

The result of the drug use investigation will be included in the PMS periodic reports. Bi-annual PMS reports will be written for the first two years and PMS annual reports will be written for the remaining years. A comprehensive PMS report will be written at the end of the drug use investigation. All analyses described will be performed on cleaned data for each bi-annual/annual report.

10.4.2. Statistical considerations for interim analyses

As this is a descriptive drug use investigation there will be no statistical adjustments required for the each bi-annual/annual analysis. The results of these analyses will not have an impact on the future drug use investigation conduct.

10.5. Statistical methods

10.5.1. Analysis of demographics/baseline characteristics

Descriptive demographic characteristics (age, height, weight, gender, and ethnicity) of the study cohort will be tabulated.

In the descriptive summary, mean, standard deviation, median, minimum, and maximum will be computed for continuous variables such as age. Frequencies and percentages will be calculated for categorical variables such as gender.

The pre-existing medical history, vaccination history within the three previous seasons (yes/no), ***concomitant medication/vaccination at least once during the 21 days (Day 0 to Day 20) follow up period*** and record years will also be presented.

The distribution of subjects vaccinated among the drug use investigation centers by years will be tabulated.

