3. STUDY DESIGN OVERVIEW

Sequential Allocation of Subject Numbers	
	Fluarix Tetra (N=max 1,440 (720 vaccinees \geq 3 years old, 720 vaccinees between 6-35 months old))
Vaccination (Fluarix Tetra)	Drug Use Investigation Conclusion 21 days (Day 0 to Day 20) follow-up after vaccination with Fluarix Tetra
N: Number of subjects planned to be enrolled	

Drug use investigation conclusion will depend on the 21 days contact of the subject in the drug use investigation. Definition of Conclusion of drug use investigation for a subject: A subject who is available for the concluding follow-up contact 21 days (Day 0 to Day 20) after receiving *Fluarix Tetra* is considered to have completed the drug use investigation.

- Drug use investigation design: A prospective, observational, non-comparative, multi-center study in Korea.
- Vaccination schedule: Vaccination as per locally approved PI (which is not part of the drug use investigation): to adults and previously vaccinated children aged \geq 6 months, a single 0.5 ml dose of *Fluarix Tetra* will be administered. To previously unvaccinated children aged 6 months to $<$ 9 years, two doses will be administered with a second 0.5 ml dose at least 4 weeks apart from the first one as per the local PI in Korea.

Fluarix Tetra may be administered to pregnant women/lactating women as per PI, if there is a clear need. Pregnancy outcome (whether full-term or premature, information on the status of the mother and child) in vaccinated pregnant subjects will be followed-up at 6-8 weeks after delivery, if possible.

Note:

- Vaccination with *Fluarix Tetra* is not part of the drug use investigation.
- Signature of the subject/subject's parent(s)/LAR(s) on the ICF/IAF signify enrolment of the subject into the drug use investigation. The ICF/IAF is for the collection and handling of safety information and not for the vaccination procedure.

- Administration of vaccines included in the EPI and other licensed vaccines are allowed in this drug use investigation regardless of the time of administration.
- Safety monitoring:
 - Recording of all AEs during the 21 days (Day 0 to Day 20) using diary cards after *Fluarix Tetra* is administered.
 - The participating physician will transcribe the collected information into the CRF in English.
 - ***Recording of all ADRs reported during the 21 days (Day 0 to Day 20) follow-up period after administration of Fluarix Tetra***

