6.3.4.1. Time window for recording concomitant medication/vaccination in the CRF

All concomitant medications, with the exception of vitamins and/or dietary supplements, administered at any time during the period starting with the administration of *Fluarix Tetra* and ending 21 days (Day 0 to Day 20) after vaccination must be recorded in the CRF.

Any vaccine not foreseen in the drug use investigation protocol administered in the period beginning 21 days (Day -20 to Day 0) preceding the dose of *Fluarix Tetra* and ending 21 days (Day 0 to Day 20) after the dose of *Fluarix Tetra* must be recorded in the CRF.

Any investigational medication or vaccine administered throughout the drug use investigation (i.e. from 21 days before the first dose of the vaccine and 21 days after administration of the dose of the vaccine) must be recorded in the CRF.

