6.5.3.4. Vaccination history

Influenza vaccine history within the three previous seasons must be recorded in the CRF. And collect information regarding all vaccines not foreseen in the protocol administered to the subject 21 days (Day -20 to Day 0) prior to vaccination with *Fluarix Tetra*.

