### 6.2 Subject characteristics

Data for the subject characteristics is demonstrated by descriptive statistics for safety analysis set.

In the descriptive statistics, number of subjects (N), mean, standard deviation, median, minimum and maximum will be calculated for continuous variables, and frequency and percentage for categorical variables.

The following subject characteristics will be reported:

< Subject baseline Information >

- Gender, Age, Height, Weight, BMI, Ethnicity, General medical history/physical examination

GlaxoSmithKline  
 Protocol No. 204687[EPI-FLU-050 VS KR PMS]

	CONFIDENTIAL : THIS DOCUMENT AND INFORMATION CONTAINED HEREIN IS PROPRIETARY TO COMPANY AND IS NOT TO BE DISCLOSED WITHOUT THE WRITTEN PERMISSION OF COMPANY.	Last Update Date 10-SEP-2021
STATISTICAL ANALYSIS PLAN(V5.0)		

(Past/Current)

< Study Medication Information >

- Vaccination history (influenza vaccination, any non-influenza vaccination), Pre-vaccination body temperature, Dose of Fluarix Tetra administration(All subjects, Subjects under age 9 years\*), Concomitant medication, Concomitant vaccination, Route of concomitant vaccination

< Special Subject Information >

- Pediatric group ( $\geq 3$  years and  $< 19$  years)\*, Elderly group ( $\geq 65$  years)\*, Pregnancy\*, Liver disorder, Kidney disorder

\* Not applicable for study group aged 6-35 months

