#### 6.3.1 Adverse Events by Subject Characteristics

For the AE(s) according to the subject characteristics\* such as gender and age in the safety assessment population:

- The number of subjects to whom AE occurred and the number of AEs will be calculated.
- The incidence proportion of AEs and its 95% confidence interval will be estimated and exploratory comparison between the group distributions will be performed using Chi-square test or Fisher's exact test. If there are two or more baseline characteristics that are statistically significant ( $p$ -value  $< 0.05$ ), they will be included in the logistic regression model to examine the effect of baseline characteristics on incidence of AEs. However, as considering the structure and characteristics of the collected data, the factors used for the actual analysis can be added or subtracted.

\* Incidence proportion for Route of concomitant vaccination and continuous variables not categorized  
 GlaxoSmithKline

	CONFIDENTIAL : THIS DOCUMENT AND INFORMATION CONTAINED HEREIN IS PROPRIETARY TO COMPANY AND IS NOT TO BE DISCLOSED WITHOUT THE WRITTEN PERMISSION OF COMPANY.	Last Update Date 10-SEP-2021
STATISTICAL ANALYSIS PLAN(V5.0)		

such as Height will be excluded from analysis.

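### Concomitant vaccination is counted on any day of the same 21 days in which AEs are counted, so the exploratory test of AE incidence by it can be biased in either direction

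*Protocol*

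**What the plan says.** - **Other vaccines are permitted at any time.** Protocol 3: "Administration of vaccines included in the EPI and other licensed vaccines are allowed in this drug use investigation regardless of the time of administration".
- **Recording.** Protocol 6.3.4.1 has other vaccines entered in the CRF if given "in the period beginning 21 days (Day -20 to Day 0) preceding the dose of" Fluarix Tetra, and again from Day 0 to Day 20 after it. Protocol 6.5.3.4 (vaccination history) asks for "all vaccines not foreseen in the protocol administered to the subject 21 days (Day -20 to Day 0) prior to vaccination" with Fluarix Tetra.
- **Definition.** The only stated analysis window for concomitant vaccination is in Protocol 10.5.1, a descriptive paragraph: "concomitant medication/vaccination at least once during the 21 days (Day 0 to Day 20) follow up period".
- **Characteristic.** SAP 6.2 lists "Concomitant medication, Concomitant vaccination, Route of concomitant vaccination" under study medication information and gives no window.
- **Test.** SAP 6.3.1 says that for subject characteristics an "exploratory comparison between the group distributions will be performed using Chi-square test or Fisher's exact test". Only route of concomitant vaccination and uncategorised continuous variables are left out, so concomitant vaccination itself stays in. SAP 6 sets two-sided 0.05. If two or more baseline characteristics are significant, they go into a logistic model for AE incidence.
- **Outcome window.** SAP 4.1 counts AEs over Day 0 to Day 20, the same days as the exposure.
- **Timing split.** SAP 6.3.3 separates by start date and by AE-treatment purpose, but for concomitant medication only.

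**The concern.** Exposure and outcome are collected over the same 21 days, and no rule requires the other vaccine to come before the AE. Two cases show the problem. A child with fever on Day 1 and another vaccine on Day 15 counts as an AE in a concomitantly vaccinated subject. A child whose next vaccine slips past Day 20 because of a Day 1 AE counts as an AE in an unvaccinated one. In both, the exposure label is settled after the outcome and may depend on it.

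A chi-square or Fisher test cannot detect this. A significant result could then enter a model whose stated purpose is the effect of baseline characteristics, although a vaccine given on Days 1 to 20 is not a baseline fact. The analysis reports go to the regulator (Protocol 10.4.1), so a falsely neutral, protective or harmful association with co-vaccination would be reported there. Protocol 6.3.4 and SAP 6.3.3 show that the sponsor has thought about timing and purpose for medication. Nothing equivalent is planned for vaccines.

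**Working it through.** **The plan's own figure.** The documents give no power or effect size for this comparison. The only precision figure is Table 4 (Protocol 10.2). Clopper-Pearson limits at n = 600 reproduce all eight rows, for example 10% gives 7.7 to 12.7 and 20% gives 16.9 to 23.4. The bias therefore has to be shown by illustration. Every input below that concerns co-vaccination, AE risk or deferral is an assumption.

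**Illustration 1: only same-day co-vaccination raises risk, and AEs start early.** A share *s* get another vaccine on Day 0 (AE risk 30%), a share *l* are due one later in the window and a share *n* get none (AE risk 20% in both). The true ratio is 0.30/0.20 = 1.5. A fraction *d* of the later-due children with an AE defer past Day 20, so 0.20·*l*·*d* moves from the exposed to the unexposed group:

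- Exposed risk = (0.30*s* + 0.20*l* − 0.20*ld*) / (*s* + *l* − 0.20*ld*)
- Unexposed risk = (0.20*n* + 0.20*ld*) / (*n* + 0.20*ld*)

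| *s/l/n* | *d* | Exposed | Unexposed | Ratio |
|---|---|---|---|---|
| 30/30/40 | 0 | 0.150/0.600 = 25.0% | 0.080/0.400 = 20.0% | 1.25 |
| 30/30/40 | 0.25 | 0.135/0.585 = 23.1% | 0.095/0.415 = 22.9% | 1.01 |
| 30/30/40 | 0.50 | 0.120/0.570 = 21.1% | 0.110/0.430 = 25.6% | 0.82 |
| 30/10/60 | 0 | 0.110/0.400 = 27.5% | 0.120/0.600 = 20.0% | 1.38 |
| 30/10/60 | 0.25 | 0.105/0.395 = 26.6% | 0.125/0.605 = 20.7% | 1.29 |
| 30/10/60 | 0.50 | 0.100/0.390 = 25.6% | 0.130/0.610 = 21.3% | 1.20 |

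A Day 0 versus no Day 0 contrast gives 30% against 20%, ratio 1.5, in every row.

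**Illustration 2: both directions.** Baseline AE risk is 10%, with 70% of AEs spread evenly over Days 0 to 2 and the rest over Days 3 to 20. Mean onset day is 0.7 × 1 + 0.3 × 11.5 = 4.15. Co-vaccination is 5% on Day 0 and 15% over Days 1 to 20 (0.75% a day). After an AE, the chance of a later vaccine is multiplied by *m*. Then

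P(exposed | AE) = 0.05 + 0.0075 × 4.15 + 0.0075 × 15.85 × *m* = 0.0811 + 0.1189*m*, and P(exposed | no AE) = 0.20.

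With no true effect:

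- *m* = 0.5: 0.0141/0.1941 = 7.2% against 0.0859/0.8059 = 10.7%, ratio 0.68.
- *m* = 0.25: 5.8% against 11.0%, ratio 0.53.
- *m* = 1: 10.0% against 10.0%, ratio 1.00.
- *m* = 2: 0.0319/0.2119 = 15.0% against 0.0681/0.7881 = 8.6%, ratio 1.74.

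At n = 600 the chance of a significant but false protective result is about 0.17 at *m* = 0.5 and 0.36 at *m* = 0.25. With a 20% baseline risk it is 0.30 and 0.64. If AEs start later (33% on Days 0 to 2) the figures fall to 0.11 and 0.21 at 10% baseline, and to 0.19 and 0.38 at 20%.

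Now let any co-vaccination add 5 points among subjects without a baseline AE. The true ratio is (0.10 + 0.05 × 0.90)/0.10 = 1.45. The any-day definition gives 0.96, 1.11, 1.45 and 2.23 at *m* = 0.25, 0.5, 1 and 2. The Day 0 contrast gives 14.5% against 10.7%, ratio 1.35, at every *m*. It is slightly diluted because its reference group still contains later co-vaccinees.

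**How common is the wrong order?** At *m* = 1, 0.1189/0.20 = 59% of co-vaccinated subjects with a baseline AE received the other vaccine after AE onset (45% if only 33% of AEs start on Days 0 to 2).

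**The case against.** **The definition is assembled from two documents.** Protocol 10.5.1 is descriptive and carries no test; Protocol 10.5.2.1 compares only age group and gender. The test is in the SAP, which gives no window. This stands as a limit on the wording. But no other definition exists, so a programmer following the plan would use Day 0 to Day 20.

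**The comparison is minor.** No objective or endpoint concerns co-administration, the investigation is descriptive, and SAP 6.3.1 calls the comparison exploratory and lets model factors be added or removed. This also stands and limits the importance. The freedom to change factors does not specify a remedy.

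**The size rests on chosen inputs.** True. In the 30/30/40 scenario, 5% deferral gives 1.20 and 10% gives 1.14. With 30/10/60 there is no reversal even at 50%. Part of the step from 1.5 to 1.25 is a change of contrast, from same-day to any-day vaccination.

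A reader might infer three stronger things that the documents do not support:

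- That the bias always runs towards the null or towards protection. It can run upward (1.74 at *m* = 2) or be absent (*m* = 1).
- That a Day 0 vaccine is counted in two analysis variables. The overlap at Day 0 is in the CRF recording windows; the SAP does not say that both variables use it.
- That concomitant vaccination will enter the logistic model. That needs two or more significant baseline characteristics, and SAP 6.2 lists this variable under study medication information, not baseline information. Entry is possible, not certain.

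**Conclusion.** The point holds for one exploratory comparison. As written, the plan classifies subjects by a vaccine that may follow AE onset, then tests AE incidence over the same days by that classification. The result can be diluted, reversed or inflated. It is unbiased only if later vaccination is unrelated to AEs and any co-vaccination carries the same risk, and the documents give no ground for assuming either.

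No single size can be stated. Under the assumptions shown, a true ratio of 1.5 reads as anything from 1.38 to 0.82, and a true ratio of 1.45 as anything from 0.96 to 2.23. These figures show what the definition allows and do not predict what the data will show.

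It would go too far to infer that the safety results as a whole are compromised. The overall and preferred-term incidences of AEs, ADRs and SAEs do not use this variable and are unaffected. The change should still be made, because it is cheap and the biased comparison would otherwise be reported.

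**What to change.** In SAP 6.2 and 6.3.1:

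1. Define the tested concomitant-vaccination variable as another vaccine given on Day 0, the day of the Fluarix Tetra dose, versus none on Day 0. Allow only this version into the logistic model.
2. For children followed for two doses, define it per dose and count AEs in the 21 days after that dose, with one table per dose so that no child enters the same test twice. State which dose supplies the value if the logistic model has one record per subject.
3. Assign Day 0 vaccines to concomitant vaccination only, and Day −20 to Day −1 vaccines to vaccination history.
4. Tabulate Day 1 to Day 20 vaccinations descriptively, without a test, showing whether AE onset came before or after that vaccination.

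**Cost.** SAP wording and a derivation from vaccination dates that the recording windows in Protocol 6.3.4.1 already require; no new visits. The Day 0 group is smaller, so its interval is wider and the test weaker. If later vaccines also raise risk, the contrast is mildly diluted (1.35 against 1.45 in illustration 2).
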